3.0 Introduction

This statistical analysis plan (SAP) describes the full (safety and efficacy) statistical analyses for venetoclax (ABT-199) Protocol M18-803 dated May 02, 2019. It will provide details of statistical methods to be followed for the study. More details in terms of analysis conventions to guide the statistical programming work will be provided in SPP (Statistical Programming Plan).

Unless noted otherwise, all analyses will be performed using SAS[®] version 9.3 or later (SAS Institute Inc., Cary, NC 27513) under the UNIX operating system.

SAP will not be updated in case of future administrative or minor amendments to the protocol unless the changes have any impact on the analysis of the study data.

4.0 Study Background

4.1 Objective

Primary Objective:

The primary objective of this study is to evaluate the efficacy of venetoclax in combination with ibrutinib in subjects with relapsed or refractory (R/R) T-cell prolymphocytic leukemia (T-PLL). Efficacy will be measured by overall response rate (ORR) in R/R subjects.

Secondary Objectives:

- Secondary efficacy analyses will be performed by the following endpoints:
 - Progression-free survival (PFS)
 - Duration of response (DoR)
 - Time-to-progression (TTP)
 - Event-free survival (EFS)
 - Overall survival (OS)

- To assess safety and tolerability in subjects with T-PLL treated with venetoclax in combination with ibrutinib. Safety will be assessed by
 - Adverse event (AE) monitoring, physical examinations, vital sign measurements, electrocardiogram variables and clinical laboratory testing.
- To assess the ability of the subset of transplant-naïve subjects to proceed to further autologous/allogeneic stem cell transplantation, will be measured by
 - Total number of eligible subjects reaching autologous or allogeneic transplantation.

Exploratory Objective:

The exploratory objective is to identify biomarker/genetically-defined subgroups regarding response and survival. Types of biomarkers may include nucleic acids, proteins, lipids, or metabolites. These biomarker assessments may be used to assess and generate prognostic, predictive, pharmacodynamics, or surrogate biomarker signatures. Analyses of biomarkers may be done as an external study report and will not be a part of the clinical study report.

4.2 Study Design

This is a Phase 2, open-label, single-arm, multicenter study designed to evaluate the efficacy and safety of venetoclax when administered with ibrutinib, in subjects with R/R T-PLL.

4.2.1 Study Design and Design Diagram

Approximately 37 subjects with T-PLL will be enrolled based on the optimal adaptive 2-stage design.¹

- Stage 1: Enroll 14 subjects with R/R T-PLL and move to Stage 2 if 4 or more responders as follows:
 - response assessment for Stage 1 will be performed on a continued basis until all 14 subjects have enrolled into Stage 1 and have completed the Week 24 disease assessment.

- Stage 2: Enroll up to an additional 23 subjects with T-PLL in Stage 2 (up to a total of 37 subjects for Stage 1 and Stage 2) depending on the number of R/R T-PLL responders at Stage 1.

Interim analysis will occur after all 14 R/R T-PLL subjects enrolled in Stage 1 of the study have completed their Week 24 disease assessments. The study will stop for futility if the number of responders at Stage 1 is ≤ 3 . If 4 or more subjects respond prior to enrolling all 14 subjects in Stage 1, enrollment will not pause between stages. The maximal sample size will be 37 subjects if number of responders at Stage 1 is 4. If there are 7 or more responders out of 14 subjects in Stage 1, 17 R/R subjects will be enrolled in Stage 2 (see Section 4.4 for details).

Subjects who are treatment-naïve (i.e., unsuitable for alemtuzumab or alemtuzumab treatment is unavailable) may be enrolled during Stage 2 of the study. The number of treatment-naïve subjects to be enrolled will depend on the required sample size for the R/R subjects in Stage 2 which is based on the number of responders from Stage 1 and considering the maximum of 37 subjects in total to be enrolled in the study.

It is to be noted that the opening of Stage 2 will be determined based on R/R T-PLL subjects, enrolled in Stage 1.

Safety will be continuously assessed and dose adjustment or tumor lysis syndrome (TLS) risk management will be considered for both venetoclax and ibrutinib.

4.2.2 Variables Used for Stratification at Randomization

This is an open-label, single-arm study. There is no randomization for this study. All subjects will be assigned a unique identification number by the IRT at the screening visit.

4.3 Endpoint

4.3.1 Primary Efficacy Endpoint

The primary efficacy endpoint in this study is ORR in R/R T-PLL subjects.

4.3.2 Secondary Efficacy Endpoints

The following are the secondary efficacy endpoints in the study: PFS, DoR, TTP, EFS, OS, total number of eligible subjects (transplant-naïve subjects who have achieved CR) reaching autologous or allogeneic transplantation.

4.3.3 Safety Endpoint

Safety data of the study will be assessed through adverse events reporting, including adverse event (AE) monitoring, laboratory values, physical examinations, vital signs, and ECG assessment. Other protocol-specified tests that are deemed critical to the safety will also be analyzed. (See Section 7.0 for analysis details).

4.3.4 Pharmacological Endpoint

Plasma samples for venetoclax and ibrutinib will be collected to determine trough concentrations (C_{trough}). A nonlinear mixed effects modeling approach may be used to estimate the population central values and the individual values of venetoclax parameters such as clearance.

4.4 Sample Size Justification

Approximately 37 subjects with T-PLL will be enrolled based on the optimal adaptive 2-stage design. In Stage 1, 14 subjects with R/R T-PLL will be enrolled and the number of responders in Stage 1 will be used to determine the number of subjects to be enrolled for Stage 2.

Sample size calculation is done based on clinical hypothesis (using optimal adaptive 2-Stage design considering 1-sided significance level of 0.05 and power of 80%): In subjects with R/R T-PLL, the treatment with venetoclax plus ibrutinib will be considered promising if the combination yields a best ORR of 40% or greater, which is the alternative hypothesis. A poor rate is defined as best ORR of 20% or less, which is the null hypothesis.

The details of the design are presented in the [Table 1](#) below:

Table 1. Sample Size Using Optimal Adaptive 2-Stage Design

H₀: p ≤ 20% versus H₁: p ≥ 40%				Comments
1-β = 80%, 1-sided test, significance level = 0.05				
n₁ = 14				
S	n₂(S)	n(S)	r(S)	
≤ 3	0	14	0	Stop for futility after Stage 1
4	23	37	11	R/R versus treatment-naïve Stage 2 sample size distribution will vary depending on the number of responses from Stage 1
5	20	34	10	
6	20	34	10	
≥ 7 ^a	17	31	9	

n₁: Sample size for Stage 1.

S: Number of responses from Stage 1.

n₂(S): Sample size for Stage 2.

n(S): Total sample size of Stage 1 and Stage 2.

r(S): Critical value of total number of responses from Stage 1 and Stage 2 to demonstrate efficacy.

- a. The Stage 2 portion will still be conducted to evaluate efficacy in additional subjects even if the Stage 1 portion shows significant efficacy.

4.5 Interim Analysis

A planned interim analysis for efficacy will be conducted after 14 subjects with R/R T-PLL enrolled in Stage 1 have completed their Week 24 disease assessments. The study will stop for futility if the number of responders at Stage 1 is ≤ 3. If 4 or more subjects respond prior to enrolling all 14 subjects in Stage 1, enrollment will not pause between stages. The maximal sample size will be 37 subjects if number of responders at Stage 1 is 4. If there are 7 or more responders out of 14 subjects in Stage 1, 17 R/R subjects will be enrolled in Stage 2.

4.6 Multiplicity Testing Procedures for Type-I Error Control

This is a Phase II hypothesis generating study; therefore, no multiplicity adjustment will be applied for the statistical analysis.

4.7 Missing Data Imputation

The missing data imputation will not be performed for this study. For time-to-event endpoints, censoring will be defined for missing data.

5.0 Analysis Populations and Important Subgroups

5.1 Analysis Population

The Full Analysis Set (FAS) includes all R/R subjects who received at least 1 dose of study drug (either venetoclax or ibrutinib). The FAS will be used for all safety, pharmacokinetic, efficacy and baseline analyses.

The analyses for the treatment naïve subjects may be conducted for similar efficacy and safety endpoints, if needed, otherwise data will be listed.

5.2 Subgroup

Subgroups will be based on demographic and baseline characteristics (age, gender, race, and high risk T-PLL factors such as tumor burden at screening; and other genetical abnormalities.). Full details will be provided in the SPP.

6.0 Efficacy Analyses

6.1 General Considerations

Efficacy will be evaluated based on clinical response criteria adapted from the response assessment criteria proposed by the international T-PLL study group. Confirmation of responses CR and CRi will be performed based on modified RECIL 2017, which is based on CT imaging (or MRI).

After the data collection is completed and reviewed for completeness and all data management quality assurance (QA) and quality control (QC) procedures are performed, the clinical database data will be extracted for documentation and statistical analyses of

the efficacy and safety data for the pre-specified cutoff date. Other considerations will be detailed in the SPP, if needed.

6.2 Primary Efficacy Analysis

Overall Response Rate (ORR) (CR + CRi + PR) will be defined as the proportion of subjects who achieved best response of confirmed complete remission (CR), confirmed complete remission with incomplete marrow recovery (CRi), or partial remission (PR) based on the clinical response criteria proposed by the international T-PLL study group as assessed by investigator up through the Week 24 disease assessment (including early study termination). The corresponding 95% confidence interval for the proportion using Binomial distribution will be constructed. Subjects who have not achieved any component of ORR will be considered as nonresponders in the calculation of ORR at the time of analysis. An interim efficacy analysis will be performed when 14 subjects in Stage 1 have completed the Week 24 disease assessments. The final primary efficacy analysis will be performed for Stage 1 and Stage 2 subjects after their completion of at least Week 24 disease assessments.

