3.2 Primary Endpoint

The primary endpoint is the ORR which is defined as the proportion of subjects achieving CR, CRi, or PR as their best overall response (per investigator assessment) in R/R T-PLL subjects based on the T-PLL consensus criteria 2019 (refer to the Operations Manual Section 3.14).^{1,11}

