7 STATISTICAL METHODS & DETERMINATION OF SAMPLE SIZE

7.1 Statistical and Analytical Plans

Complete and specific details of the statistical analysis will be described and fully documented in the SAP. The statistical analyses will be performed using SAS (SAS Institute Inc., Cary, North Carolina, USA) under the UNIX operation system.

An interim efficacy analysis will be performed when Stage 1 subjects have completed the Week 24 disease assessments in R/R T-PLL subjects.

The primary efficacy analysis will be performed for Stage 1 and Stage 2 subjects after their completion of the Week 24 disease assessments in R/R T-PLL subjects.

The final analysis will be performed when all subjects have discontinued the study or have completed protocol defined follow-up time, whichever is later.

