7.4 Statistical Analyses for Efficacy

The primary efficacy endpoint will be the ORR, defined as the proportion of subjects achieving CR, CRi, or PR as their best overall response in R/R T-PLL subjects as per investigator based on the T-PLL consensus criteria 2019.¹¹ The best overall response of CR/CRi/PR will be defined as achieving CR, CRi, and PR at any point during the study (CR/CRi will need confirmation assessment based on the T-PLL consensus criteria 2019).¹¹ The estimate and 90% confidence interval for ORR based on binomial distribution will be constructed. Subjects who have not achieved any component of ORR will be considered as nonresponders in the calculation of ORR at the time of analysis.

The secondary efficacy analysis will be based on the following endpoints: PFS, duration of response, time-to-progression, event-free survival, disease control rate, overall survival, and number of eligible subjects reaching autologous or allogeneic transplantation. All secondary endpoints will be assessed per investigator assessment in R/R T-PLL subjects based on the T-PLL consensus criteria 2019.¹¹

Time-to-event endpoints will be analyzed using Kaplan-Meier methodology. Median time-to-event and the corresponding 95% CI will be provided. Binary endpoints will be analyzed using binomial distribution and estimate of proportion along with 95% confidence interval will be provided.

Details on the primary and other efficacy analyses are provided in the SAP.

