7.6 Interim Analysis

An interim analysis for efficacy and safety will be conducted after all subjects enrolled in Stage 1 have completed the Week 24 disease assessment for the purpose of submission. The study will stop for futility if the numbers of responses at Stage 1 is ≤ 3 .

Details pertaining to the interim analyses can be found in the SAP.

A Steering Committee composed of a group of investigators who are participating in this study and who are experts in the management of T-PLL and an internal specialist in infectious diseases who is not currently involved in the conduct or oversight of Study M18-803 will review efficacy, safety, and exploratory research throughout the study.

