3.14 Disease Assessment

All measurable disease must be documented at screening (baseline) before the first dose of study drug for all subjects based on the analysis of clinical laboratory tests (hematology), physical examination, and contrast-enhanced CT scan of involved neck, chest, abdomen, and pelvis (or MRI, if CT scan is medically contraindicated).

For all subjects, clinical response (laboratory and physical examination assessments) will be assessed by the investigator during Weeks 4, 8, 12, 16, 24, 36 and every 12 weeks thereafter, and at the final visit. Note: disease assessments may be performed approximately 7 days before the scheduled visit. The clinical response will be assessed by laboratory tests and physical examination (or ultrasound) using the T-PLL consensus criteria¹ (as outlined in [Table 2](#)).

If clinical response is suggestive of a CR/CRi, a CT scan with contrast (or MRI) should be done for a confirmatory assessment as outlined in [Section 3.13](#).

If a CT scan indicates a CR/CRi, a bone marrow aspirate and biopsy will be required as soon as possible to confirm the clinical response. For subjects who opt-in for correlative biomarker analyses, a portion of the bone marrow aspirate should be split for the optional biomarker collections listed in [Section 3.17](#).

To meet the CR criteria, the CT scan and bone marrow are both required to be negative. Some subjects fulfill all the criteria for a CR but have a persistent anemia, thrombocytopenia, or neutropenia apparently unrelated to T-PLL, but related to drug toxicity. These subjects will be assessed with a response of CRi.

Disease assessment will continue to be performed after the last dose of study drug until disease progression for any subject who has not experienced PD at the time of permanent discontinuation of venetoclax and ibrutinib.

Table 2. Clinical Response Criteria (Based on Physical Examination/Ultrasound and Laboratory Tests)

Group	Parameter	Complete Remission (all met)	Partial Remission (≥ 2 in Group A and ≥ 1 in B met)	Stable Disease (all met)	Progressive Disease (≥ 1 in Group A or B met)
A	Lymph nodes by physical examination/ultrasound	All long-axis diameters to < 1.0 cm	Decrease $\geq 30\%$ in SLD	Change of -29% to $+20\%$ in SLD	Increase in $> 20\%$ in SLD from Nadir ^a

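### The SAP counts primary-endpoint responders through Week 24 and the protocol counts them at any time in the study, so the two can give different responder counts and, at a boundary, different verdicts

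*SAP*

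**What the plan says.** **Definition of response.** SAP 6.2 counts best response "as assessed by investigator up through the Week 24 disease assessment (including early study termination"). Protocol 7.4 says best overall response "will be defined as achieving CR, CRi, and PR at any point during the study". Protocol 3.2 defines the endpoint as the proportion "achieving CR, CRi, or PR as their best overall response (per investigator assessment) in R/R T-PLL subjects" and gives no time limit. Both documents require CR and CRi to be confirmed, so the window is what differs.

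**Assessments.** Operations Manual 3.14 has response "assessed by the investigator during Weeks 4, 8, 12, 16, 24, 36 and every 12 weeks thereafter". Protocol 4.1 allows up to 2 years of treatment for subjects not eligible for transplant.

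**Timing of the analyses.** Protocol 7.1: "The primary efficacy analysis will be performed for Stage 1 and Stage 2 subjects after their completion of the Week 24 disease assessments". SAP 6.2 places the primary analysis "after their completion of at least Week 24 disease assessments". Protocol 7.6 places the interim "after all subjects enrolled in Stage 1 have completed the Week 24 disease assessment". Protocol 4.1 and SAP 4.2.1 both have Stage 1 response assessed continuously until all 14 subjects have completed Week 24.

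**Versions.** The SAP (version 2.0, 17 Jul 2019) is written for the protocol of 2 May 2019. The current protocol synopsis is dated 11 November 2020, and Protocol Appendix H lists a clarification of the primary endpoint in Section 7.4. SAP 3.0 exempts the SAP from updating only where a protocol change does not affect the analysis.

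**The concern.** Subjects enrolled early can have Week 36 and later assessments on file before the last subject reaches Week 24. If one of them first responds in that interval, the protocol counts a responder and the SAP counts a nonresponder.

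This affects two decisions. The total is compared with r(S) for the efficacy verdict. The Stage 1 count S decides the futility stop and sets n2(S) and r(S). Whether S includes responses after a subject's own Week 24 is not stated, because Week 24 completion only triggers the interim.

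The any-time rule also gives unequal follow-up within one binomial test: about 24 weeks for the last subject and longer for earlier ones. The trial is open-label and investigator-assessed. With two windows on paper, the choice could be made after the responses are known.

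**Working it through.** **Inputs.** From Protocol Table 6 and SAP Table 1: n1 = 14; stop if S ≤ 3; (n2, r) = (23, 11) for S = 4, (20, 10) for S = 5 or 6, (17, 9) for S ≥ 7; null rate 20%, alternative 40%, one-sided 0.05, power 80%. The footnote to Protocol Table 6 makes 12 or more of 37 significant, so the null is rejected when the total exceeds r(S).

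**1. Reproduce the design, one window at both stages.**

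P(reject) = Σ over s = 4 to 14 of P(Bin(14, p) = s) × P(Bin(n2(s), p) ≥ r(s) + 1 − s)

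| p | S = 4 | S = 5–6 | S ≥ 7 | Sum |
|---|---|---|---|---|
| 0.20 | 0.0123 | 0.0288 | 0.0085 | 0.0496 |
| 0.40 | 0.1182 | 0.3767 | 0.3054 | 0.8003 |

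This matches the stated 0.05 and 80%. Rejecting at r(S) or more would give 0.0888 and 0.8423, so that is not the intended rule. The stated properties hold for whichever window is used, provided it is the same for S and for the total and the 20%/40% rates refer to it.

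**2. Where one late responder matters (design table only).** With S fixed at its Week 24 value, one extra responder reverses the verdict when the Week 24 total equals r(S): 11/37, 10/34 or 9/31. If the any-time rule also applies to S, a Week 24 count of 3/14 is a further such point (stop versus continue).

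| Week 24 rate | P(total = r(S)) | P(S = 3) |
|---|---|---|
| 20% | 3.9% | 25.0% |
| 30% | 9.6% | 19.4% |
| 40% | 4.2% | 8.5% |

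**3. Illustration of disagreement.** Assume that 2 or 5 percentage points of subjects first respond after Week 24. Each Week 24 nonresponder then responds late with probability late/(1 − p); at p = 0.20 this is 0.02/0.80 = 0.025 or 0.05/0.80 = 0.0625.

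- Final verdict, S fixed at Week 24: P(Week 24 total ≤ r(S) < total with late responders).
- Futility, S counted to the interim cut: P(Week 24 S ≤ 3 and S with late responders ≥ 4).

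Cells show 2 points / 5 points.

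| Week 24 rate | Verdict, late responders in Stage 1 only | Verdict, both stages | Futility, half of late responses seen | Futility, all seen |
|---|---|---|---|---|
| 20% | 0.9% / 2.4% | 2.7% / 7.6% | 3.5% / 8.8% | 7.0% / 17.7% |
| 30% | 2.5% / 5.9% | 6.4% / 14.2% | 3.0% / 7.2% | 5.8% / 13.5% |
| 40% | 1.2% / 2.7% | 2.9% / 5.5% | 1.5% / 3.4% | 2.8% / 6.1% |

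The both-stages and all-seen columns are upper bounds, because the last subject enrolled has only about 24 weeks of follow-up at the cut.

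**4. What the rates refer to.** If 40% was an any-time rate and 38% or 35% respond by Week 24, the formula in step 1 gives power of 0.7358 or 0.6177 for the Week 24 test. Conversely, if 20% respond by Week 24 and 25% at any time, and the any-time count is used throughout, the rejection probability is 0.1756.

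**The case against.** **The protocol hands details to the SAP.** Protocol 7.1, 7.4 and 7.6 all do so, and a programmer following that would use Week 24. But Protocol 7.4 states its own window, and a general deferral does not clearly let an older SAP override a definition in the later protocol.

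**Week 24 and the data cut might be the same limit.** Nonresponders in Protocol 7.4 are "considered as nonresponders in the calculation of ORR at the time of analysis", and both analyses are triggered by Week 24 completion. That sentence limits counting to the cut, not to each subject's Week 24. SAP 6.2 carries the same rule, so it does not reconcile the two.

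**The size is uncertain.** This stands. No document gives a late-response rate; if nobody first responds after Week 24 before the cut, the counts agree. The final-verdict figures hold S at Week 24. If a late Stage 1 response also moved S, for example from 4 to 5, the row would change from 37/11 to 34/10, and the final-verdict figures do not include that effect.

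**The study is hypothesis generating (SAP 4.6) and the hypothesis concerns best ORR.** The plan still sets a formal test with a futility stop, which needs one definition of a responder. Choosing Week 24 over a longer window is a design decision. Having one window is not optional.

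**The version lag is an inference.** Appendix H does not say which words were added to Section 7.4. The contradiction does not depend on its cause.

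**Conclusion.** The concern holds. Two current texts define the single primary endpoint with different windows, and nothing in either document settles which applies. The design table alone gives a 3.9% to 9.6% chance, at Week 24 rates of 20% to 40%, that the total sits where one late responder reverses the verdict. The corresponding chance for the futility stop is 8.5% to 25.0%, if the any-time rule reaches S. Actual disagreement also needs a late first responder. Under the assumed 2 or 5 points it occurs in 0.9% to 5.9% of trials for the final verdict with late responders in Stage 1 only, up to 14.2% with both stages, and up to 17.7% for the futility decision. Those percentages are illustrations; the contradiction itself needs no assumption. It must be corrected before the interim count is used.

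**What to change.** State one responder window, of the same length for every relapsed/refractory subject, in Protocol 3.2 and 7.4 and in SAP 6.2. Apply it to S at the interim and to the total compared with r(S). Week 24 fits because both analyses are triggered there. Suggested text:

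> Primary ORR is the proportion of R/R subjects in the FAS whose best response from first dose through the Week 24 disease assessment is confirmed CR, confirmed CRi or PR. The same window applies to S at the interim analysis and to the total compared with r(S) at the primary analysis.

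Report any-time ORR as supportive only, not compared with r(S). It would help to add how a CR or CRi first seen at Week 24 is counted when marrow confirmation comes later; such a subject would normally already meet PR. Re-issue the SAP against the current protocol.

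The sponsor should confirm that the 20% and 40% rates refer to the chosen window. If they were any-time rates, restate the power: about 74% if 38% respond by Week 24, 62% if 35% do. If a longer window is preferred, both analyses must wait until every subject has completed it.

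**Cost.** Wording in two documents and no new data. First responses after Week 24 would not count in the primary test, and the stated power may have to come down.
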